to attend clinic visits (days 1, 3, 8, 15 and 20) and overnight sleep lab visits (days 1, 2, 20 and 21). On every day of the treatment period, the subject will complete the CSD-M. At sleep lab visits, the subject will undergo PSG and complete the Digit Symbol Substitution Test (DSST), Karolinska Sleepiness Scale (KSS), and Profile of Mood States-Brief Form (POMSTTM-Brief). At clinic visits, subjects will complete: the Columbia-Suicide Severity Rating Scale (C-SSRS), Hospital Anxiety and Depression Scale (HADS); will undergo clinical laboratory testing, drug/alcohol screening, vital sign measurements, 12-lead electrocardiogram and a neurological exam. Adverse events and concomitant medications will be assessed. Blood samples for sparse pharmacokinetic (PK) analysis will also be collected during clinic visits.

During the washout period, (days 22 and 23) subjects will receive placebo treatment in a single-blind manner and undergo PSG testing. An end of treatment (EOT) clinic visit will be conducted on day 24.

The subject will return home and continue to complete the CSD-M [REDACTED] and will return for a clinic visit approximately 1 week after the last double-blind treatment dose to perform end of study (EOS) evaluations. A follow-up phone contact to assess safety will be done approximately 1 week after EOS visit.

Planned Number of Subjects (including sample size rationale):

Planned total number of randomized subjects is approximately 150 (~50 per treatment group) to ensure at least 30 subjects per group complete treatment.

A sample size of 30 subjects per treatment group has >80% power for detecting a statistically significant difference vs. placebo of 30 minutes (SD=45 minutes) for WASO, based on a 1-sided 2-sample t-test at 5% significance level.

Criteria for Inclusion/Exclusion:

Inclusion Criteria:

Participants are eligible if they meet all the following criteria:

1. Male or female, 18-64 years of age with a body weight of 50-100 kg (110-220 lbs) and a body mass index (BMI) of 18-32 kg/m².
2. Otherwise healthy as determined by medical evaluation that includes: medical history, physical examination, neurological exam, laboratory tests, vital signs, and cardiac monitoring.
3. History of moderate or severe alcohol use disorder (AUD) categorized based on DSM-5 criteria, as follows:
 - Moderate as defined by presence of 4-5 of the 11 criteria
 - Severe as defined by the presence of ≥ 6 of the 11 criteria.

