The washout period includes an assessment of vital sign measurements, AEs and concomitant medications. The CSD-M, DSST, KSS, POMS-Brief and C-SSRS will be completed. Study drug treatment and PSG assessments will be performed.

The end of treatment (EOT) visit consists of weight, physical and neurological exams, serum pregnancy test, C-SSRS, HADS, drug and alcohol screen, ECG, vital sign measurements, AEs and concomitant medications, CSD-M, [REDACTED] PSG, DSST, KSS, POMS-Brief, and clinical laboratory assessments.

Follow up:

The end of study visit will occur approximately 7 days after the last double-blind treatment dose and consists of vital signs, assessment of AEs and conmeds, CSD-M [REDACTED].

A follow up phone call approximately 7 days after the EOS visit will consist of an assessment of AEs and concomitant medications.

Criteria and Methods for Evaluation:

Primary Efficacy Variable:

The primary efficacy variable will be derived using 2 consecutive nights of data from polysomnography (PSG):

- Change from baseline of wakefulness after sleep onset (WASO) measured by PSG

Secondary Efficacy Variables:

The secondary efficacy variables will be derived from PSG recordings as well as CSD-M (sleep diary) data:

- SE: Sleep efficiency
- LPS: Latency to persistent sleep
- TST: Total sleep time
- NAW: Number of awakenings

The secondary efficacy variables derived from the CSD-M (sleep diary) include the following:

- sSleep: subject estimated sleep quality
- sTST: subject estimated amount of time spent asleep
- sWASO: subject estimated minutes of wakefulness during the night after initial sleep onset
- sSOL: subject estimated minutes from lights off to sleep onset
- sSE: subject estimated proportion of time spent asleep per time spent in bed derived from sTST divided by sTIB

- sNAW: subject estimated number of awakenings
- subject estimated morning sleepiness on awakening

Additional secondary efficacy variables:

- Proportion of responders derived from PSG [REDACTED]
- Rebound insomnia endpoints [REDACTED] during the washout/follow-up period

Pharmacodynamic Variables:

[figure not shown]
The pharmacodynamic variables assessing next-day residual effects:

- DSST: Digit Symbol Substitution Test
- KSS: Karolinska Sleepiness Scale
- POMS-Brief: Profile of Mood States- Brief

Safety Variables:

The safety variables assessing safety and tolerability of V117957:

- Adverse events.

Efficacy Analysis:

Analysis Populations

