Enrolled population: The group of subjects who sign informed consent.

Randomized safety population: The group of subjects who are randomized and receive at least 1 dose of the study drug and have at least 1 safety assessment.

Full analysis population: The group of subjects who are randomized, receive study drug, and have at least 1 valid efficacy measurement.

Per protocol population: The group of subjects who are included in the full analysis population but excluding those with major protocol deviations and those who do not receive the actual treatment they were randomized to receive.

Efficacy Analysis

Listings, tables, and figures of efficacy variables will be based on the full analysis population.

Primary Efficacy Analyses

Polysomnography recordings will be collected and scored by a central reader. Sleep stages will be scored following American Academy of Sleep Medicine (AASM) standard criteria based on 30-second epochs. The 2 PSG nights at baseline and post baseline PSGs performed during each sleep lab visit will be averaged before comparison.

The baseline, post baseline, and change from baseline of WASO will be summarized by treatment group using descriptive statistics and presented graphically. The statistical analysis to compare change from baseline of V117957 versus placebo will be performed by using a mixed model with factors of age group, treatment as fixed effects, baseline measurement of WASO as a covariate, and subject as a random effect. 90% confidence intervals (CIs) and P-values comparing placebo and each V117957 dose will be summarized. Plots of the least squares (LS) mean change from baseline and 90% CIs, will be produced by treatment group and visit. The impact of significant amount of missing data may be explored by using different imputation methods as sensitivity analyses.

Secondary Efficacy Analyses

The baseline, post baseline, and change from baseline of all sleep variables as measured by PSG (including TST, SE, LPS, NAW), and all sleep variables as measured by CSD-M (including sleep quality, sTST, sWASO, sSOL, sSE, etc) will be summarized by treatment group with descriptive statistics and presented graphically.

PSG data will be analyzed similarly as outlined above for the primary endpoint if they are continuous variables and follow normal distribution. Categorical endpoints will be analyzed by logistic regression or Cochran-Mantel-Haenszel test if stratified by a factor and presented graphically if appropriate.

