For CSD-M sleep diary data which will be processed into weekly data, the statistical analysis to compare change from baseline of V117957 versus placebo will be performed by using a mixed model with repeated measures (MMRM) with factors of age group, treatment, visit (first 2 nights, week 1, week 2, and week 3), and treatment-by-visit interaction as fixed effects, and baseline measurement as a covariate. 90% confidence intervals (CIs) and P-values comparing placebo and each V117957 dose will be summarized. Plots of the least squares (LS) mean change from baseline and 90% CIs, will be produced by treatment group and visit.

[REDACTED]
[REDACTED]
Pharmacodynamic Analyses 
Listings, tables, and figures of next day residual effects measured by DSST, KSS, and POMS-Brief will be based on the full analysis population. Descriptive statistics will be tabulated by treatment and presented graphically. The analysis will be performed similarly as outlined above for the primary endpoint.

[REDACTED]
Safety Analyses 
All safety data [REDACTED] will be listed for subjects in the enrolled and randomized safety populations.

AEs will be categorized into preferred terms and associated system organ class (SOC) using the Medical Dictionary for Regulatory Activities (MedDRA). Treatment-emergent AEs (TEAEs) will be defined as AEs that start after or increase in intensity after the first dose of study drug. TEAEs will be summarized by presenting the incidence of AEs for each treatment group by the MedDRA preferred term, nested within System Organ Class for the safety population. Medical history will be coded to MedDRA terms. Coded medical history terms will be summarized for all subjects in the randomized safety population.
[REDACTED] Concomitant and prior medications will be coded using the latest version of the WHO-DD and presented in tables and listings.
Interim Analysis 
After approximately half of the planned subjects have completed the end-of-study visit, an interim analysis may be performed [REDACTED] The results of the analysis will not be conveyed to the study team or to the clinical sites.

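### The next-day residual-effect tests (DSST, KSS, POMS-Brief) borrow a model with no visit or treatment-by-visit term, so one fit merges early and late effects and cannot give by-visit estimates

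*Combined protocol and SAP*

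**What the plan says.** All references are to the Synopsis of the combined protocol and SAP, the only analysis text that is visible.

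- **Pharmacodynamic Analyses.** After descriptive summaries, the inferential plan for the three tests is: "The analysis will be performed similarly as outlined above for the primary endpoint".
- **Primary Efficacy Analyses.** The model so borrowed is a "mixed model with factors of age group, treatment as fixed effects, baseline measurement of WASO as a covariate, and subject as a random effect". Plots of LS mean change with 90% CIs "will be produced by treatment group and visit". For polysomnography, "post baseline PSGs performed during each sleep lab visit will be averaged before comparison".
- **Secondary Efficacy Analyses (sleep diary).** Here the repeated-measures model names its visits and includes "visit (first 2 nights, week 1, week 2, and week 3), and treatment-by-visit interaction as fixed effects".
- **Study Design.** The tests are done at the treatment-period sleep lab visits, nights 1, 2, 20 and 21. The design then continues: "During the washout period, (days 22 and 23) subjects will receive placebo treatment in a single-blind manner and undergo PSG testing".
- **Study Procedures.** The same three tests are repeated in the washout period and at the end-of-treatment visit, which is on day 24.
- **Objectives.** Residual effect on the day after dosing is a stated secondary objective, worded as an effect of study drug.

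**The concern.** The borrowed model has one treatment term and nothing that lets the treatment effect vary by visit. Fitted once to several visits, it answers only one question: the average difference from placebo over whichever visits are included. A residual effect may differ between the first two nights and the end of three weeks of dosing, and either pattern would matter when next-day function is judged. A single term hides both.

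The listed terms also conflict with the output they are meant to support. LS means by treatment and visit need a visit term and an interaction, or a separate fit at each visit. The authors wrote both terms into the diary model, so their absence here cannot be taken as understood.

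A related gap is that the visible text does not name the mornings that form the residual-effect contrast. The tests are also done after nights on which every arm takes placebo. A difference on those mornings is not a next-day effect of a dose taken the night before.

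**Working it through.** **Plan's own figure.** No effect size, SD, correlation or power is given for these tests. The only power statement is for WASO: 30 per group, difference 30 minutes, SD 45 minutes, 1-sided 5% t-test. The noncentrality is 30 / (45 × √(2/30)) = 2.58, and power from the noncentral t is 81.8%. This agrees with the stated value above 80% and is not in dispute.

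**Step 1: terms side by side.**

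| Term | Primary model (borrowed) | Diary model |
|---|---|---|
| Age group, treatment, baseline | listed | listed |
| Visit | not listed | listed |
| Treatment-by-visit | not listed | listed |
| Random subject | listed | not listed |

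A random subject effect can be separated from residual error only if a subject has several records. PSG nights are averaged within a visit, so for PSG the term makes sense only when several visits enter one fit. That favours the single-fit reading; the by-visit plots favour the other.

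**Step 2: single fit, two on-drug visits, complete data.** With a random intercept and no visit term, visits have equal weight, so the reported effect is (d₁ + d₂)/2, where d₁ is the effect after nights 1-2 and d₂ the effect after nights 20-21.

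- Effect at one visit only: (d + 0)/2 = 0.50d.
- Same effect at both visits: (d + d)/2 = d, so nothing is lost.

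**Step 3: the weights move with dropout (illustration).** The plan randomizes about 50 per arm to secure at least 30 completers. Assume exactly 30 complete and the other 20 leave between nights 2 and 20. With variance components taken as known, a record from a subject with m visits has weight 1/(1 + (m−1)q), where q = r/(1+r) after baseline adjustment and r is an assumed correlation.

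- r = 0.5: q = 0.333 and the record weight for completers is 0.75. The early visit has 30 × 0.75 + 20 = 42.5 and the late visit 22.5. Shares are 42.5/65 = 65.4% and 34.6%.
- r = 0.8: q = 0.444. Shares are 66.2% and 33.8%.

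Under these assumptions an effect present only after nights 20-21 would be reported at about one-third of its size.

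**Step 4: which mornings follow which treatment.** Assume testing on the morning after each night; no clock time is visible. Mornings after double-blind doses are then days 2, 3, 21 and 22, and mornings after placebo nights are days 23 and 24. A sort by calendar day would put day 22 in washout although it follows double-blind night 21. A sort by the night's label would not.

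**Step 5: if post-placebo mornings entered the same single term (illustration).** Assume complete data, a constant on-drug effect d, and a washout difference of c × d. The reported effect is (2 + c)d/3. Counting mornings gives the same result, (4 + 2c)d/6.

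| c | Reported effect as a share of d |
|---|---|
| 0 (no carry-over) | 67% |
| 0.5 | 83% |
| 1 | 100% |
| 1.5 (larger difference in washout) | 117% |

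The documents give no value for c.

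**The case against.** The strongest reply is that the plan already implies visit-level analysis. The primary variable comes from two consecutive nights, PSG nights are averaged within each sleep lab visit, and plots are promised by visit. If the model is fitted at each visit, none of the shares above arises. That reading is plausible. But the text does not state it, the two nights are not named, the averaging rule is written for PSG only, and a random subject effect has no role with one averaged record per subject. The mismatch between listed terms and promised output therefore stands.

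It can also be said that an average over the two on-drug visits is a legitimate summary. It is, if chosen and labelled as such. It does not replace the by-visit estimates.

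A reader might go further and infer that the plan pools post-placebo mornings with on-drug mornings and so understates next-day impairment. The documents do not support that. No visible sentence says the mornings are pooled. The objective is limited to study drug, washout is described as a separate period with its own rebound endpoints, and redactions sit directly around the pharmacodynamic paragraph. Nor is the direction known: no carry-over would shrink a pooled estimate, while a rebound difference could sustain or enlarge it.

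Finally, the missing visit terms belong to the primary WASO model too. If that model is corrected, the correction carries over here, and only the choice of mornings remains specific to these tests.

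**Conclusion.** The point holds as a defect in the visible model statement. As listed, one fit gives a single treatment effect averaged over visits. It cannot produce LS means by visit, and with complete data it halves an effect confined to one of the two on-drug visits. That 50% follows from equal weighting and needs no assumed SD or correlation; it does assume one fit rather than a fit per visit. The shift to roughly 65% and 35% under dropout depends on the assumed r, on exactly 30 completers per arm, and on when subjects leave.

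The washout element is a request for a safeguard, not a finding of error. Two-thirds is what pooling would give with no carry-over and complete data, but neither pooling nor the direction of any bias is established. Confidence is moderate, because only synopsis text is available and redacted or fuller text may already settle which mornings are used.

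**What to change.** 1. For DSST, KSS and POMS-Brief, add visit and treatment-by-visit terms as in the diary model. Alternatively, state that the model is fitted separately at each visit; if the mornings of a visit are averaged to one record, drop the random subject effect from those fits.
2. Define the residual-effect contrasts as each V117957 dose versus placebo on the mornings after nights 1-2 and, separately, after nights 20-21.
3. As a safeguard, assign each test by the treatment taken on the preceding night, so that a test on the morning of day 22 counts with night 21.
4. Report mornings after placebo nights 22-23 separately from these contrasts.

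If redacted text already covers items 3 and 4, a cross-reference is enough. If the primary model is amended in the same way, item 1 carries over, and items 2 to 4 still need a sentence each. The cost is analysis wording only, with no added visits, assessments or subjects. The wording should be settled before unblinding so that the choice of mornings is not made with results in view.

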Full Title of the Study: A Phase 2, Randomized, Double-Blind, Multi-Center, Placebo-Controlled, Parallel-Group Study to Evaluate the Safety, Tolerability, and Efficacy of V117957 in Subjects with an Alcohol Use Disorder who are Experiencing Insomnia Associated with Alcohol Cessation	
Investigator(s)/Center(s): 20 sites	
Planned First Subject First Visit: 3Q2019	Phase of Development: Phase 2
Objectives:	
Primary: To evaluate the safety, tolerability, and efficacy of V117957 in subjects with an alcohol use disorder, who experience insomnia associated with alcohol cessation, compared to placebo.	
Secondary: Assess sleep components as measured by polysomnography, assess self-reported sleep outcomes measured by patient diary, and assess next day residual effects of study drug. [REDACTED] [REDACTED]	
Study Design (Methodology): This is a phase 2, randomized, double-blind, multi-center, placebo-controlled, parallel-group study in subjects with an alcohol use disorder (AUD), who are experiencing insomnia associated with alcohol cessation (IAAC). The total duration of the study for a given subject is up to 59 days inclusive of a 21-day screening period, 21-day treatment period, 3-day washout period, and follow-up period of up to 14 days. During the screening period subjects will be assessed to determine eligibility for enrollment in the study. Subjects complete the Consensus Sleep Diary-Morning (CSD-M) at home and if at least 3 nights of any 7-night period indicate insomnia, they will enter a sleep lab for 2 consecutive nights of polysomnography (PSG) evaluation. During the treatment period, eligible subjects will be randomly assigned to V117957 1 mg QHS, V117957 2 mg QHS or placebo QHS (approximately 50 per arm, in a 1:1:1 ratio). Eligible subjects will be required	

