Reference Treatment, Dose, and Mode of Administration:

All doses will be administered with water in the evening at bedtime, at least 1 hour after the last meal of the day, for up to 23 consecutive nights (21 nights during the double-blind treatment period to subjects assigned to placebo and for 2 nights during the washout period to all subjects).

- Placebo tablet, oral administration
Subjects assigned to placebo will take 2 placebo tablets

Concomitant Medication:

Medications for chronic conditions, such as antihypertensives, lipid lowering agents, acetaminophen, NSAIDs and vitamins, are allowed as long as the subject is on a stable regimen throughout their study participation.

Duration of Treatment and Study Duration:

Total study duration is approximately 59 days.

Screening period is up to 21 days; double-blind treatment period is 21 days; washout period is 3 days; and the follow-up (safety) period is approximately 14 days.

Study Procedures:

Screening period (up to 21 days):

The screening period is 21 days prior to randomization. Screening activities consist of demography, medical and medication history, physical and neurological exam, 12-lead electrocardiogram (ECG), and vital sign measurements (systolic/diastolic blood pressure, pulse rate, respiratory rate, and oral temperature), pulse oximetry (SpO2), drug and alcohol screen, hepatitis B and C screen, serum pregnancy test (females only), FSH test for post menopausal women, clinical laboratory assessments, inclusion/exclusion criteria evaluation (including completion of the C-SSRS), the CSD-M including assessment of insomnia [REDACTED]. If the CSD-M shows insomnia the subject should be scheduled for PSG testing to confirm insomnia.

Double-blind treatment period:

Treatment activities consist of a urine pregnancy test (females only), C-SSRS, HADS, drug and alcohol screen, neurological exam, ECG, vital sign measurements, AEs and concomitant medications, CSD-M, [REDACTED] PSG tests – 2 at the beginning and 2 at the end of the period, DSST, KSS, POMS-Brief, clinical laboratory assessments, sparse PK sampling and receive study drug treatment. During the double-blind treatment period subjects will be dosed in the sleep lab and will take medication home with them for daily nighttime dosing. Subjects will return to the clinic on days 8, 15 and 20 for study procedures.

Washout period:

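### The visible TEAE rule has no closing day and no split by study period, so adverse events in the placebo washout and follow-up are counted in the same table as events on V117957

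*Combined protocol and SAP*

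**What the plan says.** The Synopsis (Safety Analyses) defines TEAEs as "AEs that start after or increase in intensity after the first dose of study drug". The next sentence gives the summary: "TEAEs will be summarized by presenting the incidence of AEs for each treatment group by the MedDRA preferred term", nested within system organ class, in the safety population. Neither sentence gives a last day or mentions a study period. The Analysis Populations section defines the randomized safety population as "The group of subjects who are randomized and receive at least 1 dose of the study drug and have at least 1 safety assessment".

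The timing comes from other parts of the Synopsis:

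- Duration of Treatment and Study Duration: "double-blind treatment period is 21 days; washout period is 3 days", and "the follow-up (safety) period is approximately 14 days".
- Study Design, on days 22 and 23: "subjects will receive placebo treatment in a single-blind manner and undergo PSG testing". The Reference Treatment section confirms that these two placebo nights apply to every arm.
- Study Procedures: adverse events are assessed during washout, at the end-of-study (EOS) visit about 7 days after the last double-blind dose, and once more after that: "A follow up phone call approximately 7 days after the EOS visit will consist of an assessment of AEs and concomitant medications".

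The full title sets the trial "to Evaluate the Safety, Tolerability, and Efficacy of V117957", and the primary objective likewise includes safety and tolerability. Adverse events are the one safety variable listed.

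**The concern.** Read literally, an event that begins on a washout placebo night, or in the following days at home, is a TEAE of the V117957 group and sits in the same row as an event that began on drug. The table then shows neither the incidence on treatment nor the incidence after stopping.

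The plan does separate these phases for efficacy. The diary model stops at week 3, and rebound insomnia has its own endpoints in the washout and follow-up. No matching separation is visible for adverse events.

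At stake is how a tolerability signal is read in a trial of about 50 subjects per arm. An on-drug excess may look smaller in relative terms, and an excess that appears only after stopping may be taken for an effect of treatment.

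**Working it through.** **1. Length of the window.** The stated total reproduces: 21 screening + 21 treatment + 3 washout + 14 follow-up = 59 days. There are two ways to count the days off drug:

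- By the visit schedule, the last double-blind dose is on day 21, EOS is about day 28 and the call about day 35. Off drug: 7 + 7 = 14 days; 14/35 = 40%.
- By the period lengths: 3 + 14 = 17 days; 17/38 = 45%.

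With 21 days of screening, the visit schedule totals 21 + 35 = 56 days, 3 fewer than 59. The stated durations are approximate or upper limits, which may cover the difference, but the two counts should be reconciled.

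**2. Rate ratio if the off-drug hazard returns to background.** With true on-drug rate ratio r and d off-drug days, the pooled ratio = (r × 21 + d)/(21 + d).

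- d = 14: r = 2.0 gives (42 + 14)/35 = 1.6; r = 3.0 gives (63 + 14)/35 = 2.2.
- d = 17: r = 2.0 gives (42 + 17)/38 = 1.55; r = 3.0 gives (63 + 17)/38 = 2.11.

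**3. Incidence on both scales.** The documents give no adverse event rates, so these are assumptions. Take a 20% placebo incidence over 35 days, a constant hazard, and r = 2.

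- Days 1–21: placebo 1 − 0.8^(21/35) = 12.5%; active 1 − 0.8^(42/35) = 23.5%. Ratio 1.87, difference 11.0 points.
- Pooled 35 days: placebo 20.0%; active 1 − 0.8^(56/35) = 30.0%. Ratio 1.50, difference 10.0 points.

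**4. Range.** Let p0 and p be the assumed 21-day incidences on placebo and active. The open-window incidence is q = 1 − (1 − p)(1 − p0)^(14/21), with p = p0 for placebo.

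| Placebo vs active, 21 days | Ratio, closed → open | Difference in points, closed → open |
|---|---|---|
| 5% vs 15% | 3.00 → 2.18 | 10.0 → 9.7 |
| 10% vs 20% | 2.00 → 1.58 | 10.0 → 9.3 |
| 20% vs 40% | 2.00 → 1.55 | 20.0 → 17.2 |
| 30% vs 45% | 1.50 → 1.26 | 15.0 → 11.8 |

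With 17 off-drug days the open-window ratios are 2.08, 1.53, 1.50 and 1.24.

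**5. The opposite case: withdrawal events and no on-drug effect.** Assume a 10% background per 21 days and, in the active arm, an added independent 10% risk in the 14 off-drug days. The background-free probability over 14 days is 0.9^(14/21) = 0.932.

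- Off-drug table: 1 − 0.932 × 0.9 = 16.1% vs 1 − 0.932 = 6.8%, ratio 2.37.
- Pooled table: 1 − 0.9 × 0.932 × 0.9 = 24.5% vs 1 − 0.9 × 0.932 = 16.1%, ratio 1.52.

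The true on-drug ratio here is 1. A reader of the pooled table would see 1.52 and could not tell that all of it arose after stopping.

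**6. Early stoppers.** EOS is timed from the last double-blind dose. A subject who stopped on day 10 (illustrative) and kept to that timing would have 14 of 24 days, 58%, off drug.

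**The case against.** A reader might infer that the trial has no by-period adverse event table at all, that withdrawal effects are hidden, or that pooling always dilutes a drug effect. The documents do not support any of these.

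- Parts of the safety section are redacted and the supplied text is a synopsis. Silence in the visible text does not show that a by-period table is not planned.
- The text says treatment group. It does not say whether subjects are grouped as randomised or as treated.
- The window is open in the definition, but collection ends in practice with the follow-up call.
- Rebound insomnia is a named secondary endpoint. Next-day effects have the DSST, KSS and POMS-Brief, which are also completed in washout, as is the C-SSRS. Safety data are listed too.
- Dilution requires the off-drug hazard to return to background. Withdrawal events push the active-arm total up, so the two harms are alternatives with opposite directions.
- The risk difference moves less than the ratio. In step 3 it moves by about 1 point, against a standard error of √(0.30 × 0.70/50 + 0.20 × 0.80/50) = 8.6 points with 50 per arm. The visible plan has no adverse event hypothesis test to distort.
- The documents give no half-life, so treating day 22 onward as free of drug is itself an assumption.

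All of this stands and limits the point. It does not answer the core: the two intact sentences on TEAEs, followed as written, put on-drug and off-drug events in one table, and adverse events other than rebound insomnia have no visible separate summary.

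**Conclusion.** The point holds in a limited form. In the visible text the TEAE window has no closing day, and the described table pools 21 days of double-blind treatment with about 14 days (40% of the window) or 17 days (45%) after it.

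Under a return to background hazard, the relative measure shrinks clearly: a rate ratio of 2.0 to about 1.6, or an incidence ratio of 1.87 to 1.50. The absolute difference shrinks modestly: about 1 point in that example, and 0.3 to 3.2 points over the rates in step 4. If withdrawal events occur, they are misattributed to treatment. All event rates are assumed.

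This is a reporting weakness in a primary objective. It does not make the analysis invalid. It is worth correcting because the correction costs little.

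**What to change.** 1. Keep the overall TEAE table.
2. State when the TEAE window closes, and reconcile the 14-day and 17-day counts.
3. Add the same incidence table split by onset (or worsening) into the double-blind period and the washout/follow-up period. Anchor the split to each subject's last double-blind dose, so that subjects who stop early are classified correctly.
4. Use the first part for the on-treatment comparison and the second for events after stopping.

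The cost is a few lines of SAP text and one more table, from onset and dosing dates that adverse event reporting already needs. No visit or procedure changes. There are two downsides. Events near the boundary need an onset time. And, with no half-life in the documents, early washout events may still reflect residual drug, which a footnote to the second part should say.
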